3. Record the adverse effects of the different pharmacological therapies reported in the different groups throughout their follow-up.
4. Evaluate the lung function of the different groups at 3 months after discharge, 6 months and 12 months after discharge.

METHODS

a) Location of the study.

National Institute of Respiratory Diseases, Ismael Cosío Villegas México.

Smoking and COPD Research Department.

b) Description of the population:

Inclusion criteria:

1. Over 18 years of age.
2. Active smokers (smoking more than 100 cigarettes in their entire life and having consumed cigarettes in the last 30 days)
3. Hospitalized subjects with acute or chronic lung disease.
4. Signing of informed consent.

Exclusion criteria:

1. Subjects with pharmacological treatment to stop smoking during recruitment or in the last month.
2. Contraindications to the use of pharmacological therapy. (Annex is attached the contraindications for the use of medications)
3. Subjects who cannot maintain follow-up.

Elimination criteria:

1. In an analysis by intention to treat, there will be no elimination of subjects after randomization.

Sample size:

The sample size calculation is carried out by difference between proportions, with a confidence level of 95%, power of 80%, unilateral, with an observed proportion of 65% and an expected proportion of 80% for the combination of pharmacological therapy; 50 subjects are required for each group; If a loss of participants is estimated at 25%, 67 subjects are required for each group. The sample size was carried out in the WinEpi 2006 program.

c) Outcome variables and description of other study variables.

Outcome variable:

-Abstinence: abstinence from tobacco is defined as its suspension 12 months after hospital discharge, corroborated by detection of exhaled carbon monoxide less than 7 ppb and/or detection of cotinine in urine (positive).

-Active smoker: defined as an active smoker who has consumed more than 100 cigarettes in his or her entire life and who has consumed cigarettes in the last 30 days.

-CBT (cognitive behavioral therapy) is a model for treating problematic behaviors that focuses primarily on identifying and changing maladaptive patterns of behavior and thoughts, including problem-solving and coping skills rooted in relapse prevention theory, along with the cognitive restoration of maladaptive thoughts to regulate emotions and is combined with the recommendations of the Clinical Practice Guideline (CPG) for tobacco.

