(14)

-Acute or chronic lung disease: Acute or chronic lung disease will be considered by medical diagnosis.

-Exhaled carbon monoxide: a value greater than or equal to 7 ppb is defined as positive (subject with active smoking).

-Cotinine in urine: defined as positive (subject with active smoking) positive test (qualitative test)

-Nicotine dependence (Fagerström Questionnaire): mild, moderate and severe.

-Withdrawal symptoms questionnaire.

-Nicotine Craving Questionnaire (Urge to smoke, understood as a physiological and motivational state that drives the desire to smoke tobacco).

-Adverse reactions questionnaire.

-Respiratory symptoms questionnaires (PLATINO).

-Pulmonary function tests (pre- and post-bronchodilator spirometry, carbon monoxide diffusion, and 6-minute walk)

-Beck Anxiety and Depression Questionnaires.

Procedures for collecting information using instruments and data quality control methods.

Data Capture.

a)

b) 1-Subject identification (inclusion/exclusion criteria)

c) 2-Signature of informed consent

d) 3-Randomization of the drug (2 groups: a-nicotine patches, b-combination: nicotine patches + bupropion)

e) 4-Start hospitalization treatment

f) - Processes: Medications are given in a personalized way during hospitalization; brief advice is given, and questionnaires and measurements of exhaled CO and cotinine in urine are performed (treatment start day is day 0). The pharmacological treatment given to the subject will be for at least 12 weeks.

g) 5-Monitoring during hospitalization to provide medications

- h) 6-Upon discharge, an appointment is made at the Smoking Clinic within the first 14 days of discharge, and anti-smoking treatment for home use and brief advice will be provided.
- i) 7-First appointment at the Smoking Clinic
- j) - Processes: brief advice; intake of exhaled CO and cotinine in urine). It is scheduled to begin cognitive behavioral therapy (CBT) in a group, which lasts ten sessions, two times a week, with mixed modality (online or in-person).
- k) 8-Start CBT in the next two weeks after discharge.
- l) 9- Second appointment at the Smoking Clinic at the end of therapy (3 months after discharge)
- m) - Processes: brief advice; questionnaires and measurement of exhaled CO and cotinine in urine are performed; pre- and post-bronchodilator spirometry, carbon monoxide diffusion, 6-minute walk.
- n) 10-Third appointment at the Smoking Clinic 6 months after discharge:

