- o) - Processes: brief advice; questionnaires and measurement of exhaled CO and cotinine in urine are performed; pre- and post-bronchodilator spirometry, carbon monoxide diffusion, 6-minute walk)
- p) 11-Fourth appointment at the Smoking Clinic 12 months after discharge
- q) - Processes: brief advice; questionnaires and measurement of exhaled CO and cotinine in urine are performed; pre- and post-bronchodilator spirometry, carbon monoxide diffusion, 6-minute walk)
- r) The information collection will be carried out through the INER RedCAP platform, which has security mechanisms for the data obtained and methods for adequate control. The protocol researchers will carry out data capture.

Results analysis plan.

1- A retrospective analysis was carried out on hospitalized patients with a history of active smoking, with the following characteristics: 40% of the patients evaluated had low dependence on nicotine, and 60% had moderate and severe dependence. Of the patients evaluated, 72% were male, and 28% were female. Proportional allocation is carried out for stratified sampling, Stratified randomization for sex (man and woman), and for low and moderate/severe dependence

2- Statistical analysis methods according to the type of variables: the variables will be analyzed according to their type of distribution and whether they are quantitative or qualitative, by student's t or chi2 as appropriate. A descriptive analysis will be carried out on each of the variables. Subsequently, a comparative analysis will be carried out between the 2 groups included, using ANOVA or Kruskal Wallis, depending on their distribution. The analysis of the main objective will be carried out by intention to treat according to the treatment granted and randomization. Randomization was stratified by level of nicotine dependence and sex. There will be no blinding. The primary outcome will be abstinence at 12 months, and its association with the randomized treatment group will be seen. As a complementary analysis, a per-protocol analysis will be performed according to the treatment received. Finally, through multivariate analysis by logistic regression, abstinence or non-abstinence at one year was analyzed depending on the treatment received, adjusted for the different covariates such as sex, age, smoking rate, and level of dependence.

3-The statistical analysis will be carried out using the STATA V13 statistical package.

ETHICAL CONSIDERATIONS

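### The exhaled CO cut-off that verifies 12-month abstinence is given as 7 ppb (0.007 ppm), which on assumed CO levels in abstainers only a reading of 0 would meet

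*Combined protocol and SAP*

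**What the plan says.** The cut-off appears twice in METHODS, part c (outcome variables and description of other study variables).

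- The abstinence entry requires that stopping tobacco be "corroborated by detection of exhaled carbon monoxide less than 7 ppb and/or detection of cotinine in urine (positive").
- The exhaled carbon monoxide entry gives the complement: "a value greater than or equal to 7 ppb is defined as positive (subject with active smoking").

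The two entries agree on number, unit and direction, and ppm appears nowhere in the documents. The Results analysis plan makes this definition decisive: "The primary outcome will be abstinence at 12 months". The CO reading that serves it is taken at the "Fourth appointment at the Smoking Clinic 12 months after discharge". CO is also measured in hospital, at the first clinic appointment, and at 3 and 6 months. The documents name no CO monitor, resolution or display unit, and give no source for the cut-off.

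**The concern.** A threshold of 7 ppb is a very small concentration. If abstainers' breath normally contains CO at the level of whole or half parts per million, the written rule lies far below anything an abstainer would produce and cannot separate abstainers from smokers. The natural explanation is a unit slip, written once and repeated when the same rule was stated from the other side. Agreement between the two entries is therefore no evidence that the unit is right.

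The rule matters because it classifies the primary outcome and the trial is unblinded, so biochemical verification is the main protection against biased self-report. If a database field or derivation followed the protocol text literally while the monitor reported ppm, abstainers in both arms would be recorded as smokers by CO. Specific objective 1 also looks at 3 and 6 months, so the same cut-off may be used there, although the primary outcome is at 12 months only.

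**Working it through.** The cut-off is a definition, so there is no calculated figure in the plan to reproduce. The check is a unit conversion, followed by classifying a range of CO values under each unit.

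**Inputs**
- Written cut-off: below 7 ppb is abstinent, 7 ppb or more is active smoking (METHODS, part c, both entries).
- Conversion: 1 ppm = 1000 ppb.
- Assumption, not in the documents: the monitor reads in ppm.
- Assumption, not in the documents: abstainers exhale about 0.5 to 6 ppm. Values from 0 to 10 ppm are tested.

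**Conversion**
- 7 ppb = 7 / 1000 = 0.007 ppm.
- 7 ppm / 7 ppb = 7000 ppb / 7 ppb = 1000.

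**Classification by CO alone**

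| Exhaled CO (ppm) | In ppb | Cut-off 7 ppb (as written) | Cut-off 7 ppm (if ppm was meant) |
|---|---|---|---|
| 0 | 0 | abstinent | abstinent |
| 0.05 | 50 | active smoker | abstinent |
| 0.5 | 500 | active smoker | abstinent |
| 1 | 1000 | active smoker | abstinent |
| 3 | 3000 | active smoker | abstinent |
| 6 | 6000 | active smoker | abstinent |
| 6.9 | 6900 | active smoker | abstinent |
| 7 | 7000 | active smoker | active smoker |
| 10 | 10000 | active smoker | active smoker |

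The unit changes the class only for readings from 0.007 ppm up to, but not including, 7 ppm. The whole assumed abstainer range falls in that interval.

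**Sensitivity to the assumption**
- Low end of the assumed range against the written cut-off: 0.5 / 0.007 = about 71.
- Lowest non-zero value in the table: 0.05 / 0.007 = about 7.

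The assumed low end would have to be too high by a factor of about 71 before an abstainer at that level could pass on a non-zero reading.

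**When the slip takes effect**
- Staff compare the number on a ppm display with 7: the classes are those of the last column, and nothing is lost.
- Readings are converted to ppb, or a database rule converts them, and are then compared with 7: the classes are those of the third column, and only a 0 passes.

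The documents say that data are captured by the researchers in RedCAP. They do not say which of these would happen.

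**The case against.** The strongest reply is that nothing in the documents contradicts the unit. Both entries say ppb, no ppm cut-off appears, and no device or CO value is given, so the error is inferred from assumed values. In practice, staff would probably read a ppm meter and compare it with 7, and no patient would be misclassified. On that view this is a label to tidy up.

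Much of this stands. The point does rest on stated assumptions, and the harm is conditional. It does not remove the point, because the conclusion survives a very wide range of assumed CO values. This is also the operative rule for the primary endpoint, and the plan gives a reader no means of settling the unit.

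Several stronger readings are tempting, and the documents do not support them:

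- **That no patient could be classed abstinent by CO.** A reading of 0 is below 7 ppb and passes.
- **That CO results would be wrong for all patients.** Readings of 0, and of 7 ppm or more, keep their class under either unit.
- **That overall abstinence would fall to near 0% against the planned 65% and 80%.** The abstinence entry joins CO to cotinine by and/or, so failing CO does not alone settle the outcome. The sample-size paragraph does not call 65% and 80% CO-verified rates.
- **That the documents establish 7 ppm as the intended value.** They do not. It follows only if the monitor reads in ppm.

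The cotinine route is no firm fallback. The abstinence entry lists a positive cotinine result as corroboration, whereas the cotinine entry reads "defined as positive (subject with active smoking) positive test (qualitative test"). That is a separate contradiction, but it leaves CO as the only verification test stated in a consistent direction.

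**Conclusion.** The point holds as a probable unit error in the rule that verifies the primary outcome. The written cut-off is 0.007 ppm, exactly 1000 times below 7 ppm. Assuming a monitor that reads in ppm and abstainers who exhale about 0.5 to 6 ppm, the rule applied literally classes almost every abstainer as an active smoker by CO, and only a reading of 0 passes. The conclusion is unchanged for values down to 0.05 ppm.

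It is limited to the CO route at the 12-month assessment, and to any earlier visit where the same cut-off is used. It does not show what the overall abstinence rate would be, or that any result would actually be misclassified, since that depends on how readings are compared with the threshold. The correction should be made because the rule is decisive and cheap to put right, but the effect on the trial is possible and not demonstrated.

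**What to change.** 1. Confirm the display unit of the CO monitor in use, and name the device and unit in the protocol.
2. Correct the unit in the abstinence entry and the exhaled carbon monoxide entry together, so that they remain complementary. If the device reads ppm, the unit becomes ppm and the cut-off becomes 7 ppm. If it reads in another unit, state the cut-off in that unit with its source.
3. Label the RedCAP field with the same unit, add a range check, and base any derived smoking status on that unit.
4. Do this before outcomes are classified. If CO values have already been entered, check which unit was used.

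The cost is one word in each of two definitions, a field label and a range check. Treatment, visits and sample size are unaffected.

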Nicotine Replacement Therapy (NRT) helps combat nicotine withdrawal symptoms by providing users with nicotine in long-acting (patch) or short-acting (mask gum, lozenges, inhaler, nasal spray) form. Use of NRT in any form increases smoking abstinence by 60% compared to placebo (RR 1.60, 95% CI 1.53–1.68). To increase effectiveness, the nicotine patch can be combined with short-acting NRT, which is more effective than using a form of NRT (RR 1.34, 95% CI 1.18–1.51) (10). Bupropion increases norepinephrine and dopamine levels and is approved as an antidepressant for smoking cessation. Increases smoking cessation rates compared to placebo (OR 1.75, 95% CI 1.52 to 2.01) (8.9). Varenicline is a partial nicotinic receptor agonist that doubles smoking abstinence rates compared to placebo (RR 2.24, 95% CI 2.06–2.43). (10) These results have been obtained in smokers treated on an outpatient basis. The study of the effectiveness of these different treatments in hospitalized subjects has been little and marginally analyzed.(6) Among the studies carried out, it shows that hospitalized subjects who received treatment for smoking cessation and support had abstinence rates greater than 6 months. The analysis carried out in this study does not differentiate by type of pharmacological treatment. The predominant pharmacological treatment was NRT. (11) Smoking cessation in hospitalized patients has been associated with lower rates of postsurgical complications, better tissue healing and proliferation, and reversibility of the attenuation of inflammation mechanisms. (12,13)

Hospitalization is a vital scenario to address tobacco consumption for various reasons and benefits; among the most important are the prohibition of smoking on the hospital premises and the special availability for quitting that the smoker has during admission to a hospital admission promotes subsequent tobacco cessation because a severe illness, primarily if related to tobacco, can increase smokers' motivation to quit.

MAIN OBJECTIVE

Our objective will be to analyze the effectiveness of the combination of bupropion and nicotine versus nicotine replacement therapy to quit smoking in hospitalized subjects 12 months after discharge.

SPECIFIC OBJECTIVES

1. Analyze the effectiveness of the combination of pharmacological therapies to quit smoking in hospitalized subjects 3, 6 and 12 months after discharge.
2. Evaluate the symptoms and signs of withdrawal in the different groups throughout their follow-up.

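### Urine cotinine is coded as active smoking although both arms receive nicotine patches, and the abstinence definition does not settle which test decides; abstinent patch users may be counted as smokers, mainly at 3 months

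*Combined protocol and SAP*

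**What the plan says.** All references are to the combined protocol and SAP.

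- **Arms** (Data Capture, step 3): "2 groups: a-nicotine patches, b-combination: nicotine patches + bupropion". Patches are therefore given in both groups.
- **Duration** (Data Capture, step 4): "The pharmacological treatment given to the subject will be for at least 12 weeks", counted from hospital ("treatment start day is day 0"). No upper limit is given.
- **Coding of the tests** (Methods, section c): the urine cotinine entry reads "defined as positive (subject with active smoking) positive test (qualitative test". The exhaled CO entry reads "a value greater than or equal to 7 ppb is defined as positive (subject with active smoking". Neither mentions patch use.
- **Abstinence** (Methods, section c): cessation 12 months after discharge, "corroborated by detection of exhaled carbon monoxide less than 7 ppb and/or detection of cotinine in urine (positive". This is the only definition of abstinence in the plan.
- **Visits** (Data Capture, steps 7 and 9 to 11): CO and urine cotinine are measured at the first clinic appointment and at 3, 6 and 12 months. The 3-month visit is described as "Second appointment at the Smoking Clinic at the end of therapy (3 months after discharge".
- **Objectives**: specific objective 1 asks for effectiveness in "hospitalized subjects 3, 6 and 12 months after discharge". The Results analysis plan sets 12-month abstinence as the primary outcome and states that the trial is not blinded.

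**The concern.** Cotinine is a metabolite of nicotine. A qualitative test returns positive or negative and carries no information on whether the nicotine came from a patch or from tobacco. In a trial that gives patches to everyone, a rule that reads every positive as smoking can label an abstinent patient who is using the study treatment as a failure.

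Two features of the text make this more than a missing detail. First, the abstinence sentence and the cotinine entry give a positive test opposite meanings. Second, the and/or leaves open whether CO alone is enough, whether both tests must agree, or whether cotinine can decide. Abstinence at 3 and 6 months has no definition of its own, so the test codings are the only biochemical rules available for those visits.

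At stake are the level of the reported abstinence rates, the size of the absolute difference and the power to detect it. If patch use at a visit differs between arms, which is possible in an open-label trial, the direction of the comparison is at stake too.

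**Working it through.** **Step 1. How the wording classifies an abstinent patient on patches (CO below the cut-off, cotinine positive).**

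| Reading of the abstinence sentence | Classified as |
|---|---|
| CO below the cut-off is enough | abstinent |
| CO below the cut-off and a negative cotinine both required | smoker |
| Cotinine decides, coded as in the cotinine entry | smoker |
| As printed, a positive cotinine supports abstinence | abstinent |

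The same patient is classified two ways, and the plan does not choose. Under the last reading a positive test in someone who is smoking would also support abstinence, which cannot be intended.

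**Step 2. Who could be on patches at each visit.**

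- First appointment, planned within 14 days of discharge: patients following treatment are on patches. This is not an effectiveness time point.
- 3 months: the minimum course is 12 × 7 = 84 days from day 0 in hospital. Three months after discharge is about 91 days plus the inpatient stay. A patient treated for exactly the minimum has stopped by then. Because 12 weeks is only a minimum, and the visit is tied to the end of therapy, patch use at or near the visit remains possible.
- 6 and 12 months: patch use is neither planned nor excluded.

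**Step 3. Worst-case size.** The plan states no figure to reproduce here. Assume that cotinine decides, that every patch user tests positive, and that a share f of true abstainers is on patches at the visit. The documents give no value for f. The 65% and 80% come from the sample size paragraph, which attaches no time point to them.

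Observed abstinence = true abstinence × (1 − f). At f = 20%: 0.65 × 0.80 = 0.52 and 0.80 × 0.80 = 0.64.

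Power is one-sided at 5% with n = 67 analysed per group: Φ{[d√n − 1.645√(2p̄(1−p̄))] / √(p₁(1−p₁) + p₂(1−p₂))}, where p₁ and p₂ are the observed rates, d is their difference and p̄ their mean.

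| f, equal in both arms | Patches alone | Combination | Difference (points) | Power |
|---|---|---|---|---|
| 0 | 65.0% | 80.0% | 15.0 | 62% |
| 10% | 58.5% | 72.0% | 13.5 | 50% |
| 20% | 52.0% | 64.0% | 12.0 | 41% |
| 30% | 45.5% | 56.0% | 10.5 | 33% |
| 50% | 32.5% | 40.0% | 7.5 | 23% |

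The ratio of patches alone to combination does not move: 0.65/0.80 = 0.52/0.64 = 0.8125. (Power at f = 0 is below the planned 80%; that belongs to the sample size calculation and is not part of this point.)

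**Step 4. Unequal patch use.**

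- No true effect, 65% in both arms, with 30% (patches alone) vs 15% (combination) still on patches: 0.65 × 0.70 = 45.5% and 0.65 × 0.85 = 55.3%, a spurious difference of about 10 points. Swapping the shares reverses its sign.
- True 65% vs 80%, with 20% vs 30% on patches: 0.65 × 0.80 = 52% and 0.80 × 0.70 = 56%, so 15 points shrink to 4.
- The same truth with 30% vs 20%: 0.65 × 0.70 = 45.5% and 0.80 × 0.80 = 64%, so 15 points grow to 18.5.

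**The case against.** The strongest reply is that the cotinine entry codes a test result and is not the outcome rule. The sentence that defines abstinence allows CO alone to confirm it, and on that reading no patch user is misclassified. This stands as a limit: a reader might infer that patch users will be counted as smokers, but the documents support only that they may be, depending on how and/or is read. It does not remove the point, because the plan leaves the reading open and the two entries contradict each other.

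Second, the minimum course ends before the 3-month visit, and the reference to the end of therapy follows directly on the steps for group behavioural therapy, so it may not mean patches. The timing is correct for patients treated for exactly 12 weeks. The behavioural reading fits poorly: ten sessions at two a week take five weeks, starting within two weeks of discharge, so they would end near week seven. Exposure at 3 months is therefore possible but not established.

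Third, both arms receive patches, so the error might be thought to cancel. With equal patch use the risk ratio is indeed unchanged and no false effect arises, but the absolute difference and the power still fall. With unequal use nothing cancels.

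Fourth, the contents of the visit questionnaires are not shown, so they may already record nicotine-product use. That cannot be judged from the documents.

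**Conclusion.** The point holds in a limited form. The plan gives nicotine to both arms, codes a nicotine metabolite as evidence of smoking without exception, and contradicts itself on what a positive result means. Whether abstinent patch users are misclassified depends on an unresolved and/or: they are if a negative cotinine is required or cotinine decides, and they are not if CO alone suffices.

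The exposure falls mainly on the 3-month result under specific objective 1 and less on the 6-month result. A reader might infer that the primary outcome is compromised; the documents do not support that, since 12-month abstinence is affected only if patches are still in use a year after discharge. Nor should the illustrative 10-point spurious difference be read as a forecast: it rests wholly on an assumed imbalance in patch use, and the bias could go either way. All the sizes above are worst cases with assumed shares.

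Confidence is high in the measurement problem and the contradiction, and lower in the classification and size that would result. This should be corrected before the 3-month data are analysed.

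**What to change.** 1. Reconcile the abstinence sentence with the cotinine entry in Methods, section c), so that a positive cotinine never supports abstinence.
2. Replace and/or with one rule, applied at 3, 6 and 12 months in both arms, and state the self-report window. The plan's active-smoker definition already uses 30 days.
3. Record current nicotine-product use at each visit, if the questionnaires do not already do so.
4. In anyone using a nicotine product at or near the visit, verify abstinence by self-report plus exhaled CO below the plan's cut-off. In patients off nicotine products, require a negative urine cotinine as well.

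The cost is a rewritten outcome definition and at most one added question per visit. Both tests are already scheduled, and no treatment changes. The downside is that CO covers a shorter period than cotinine, so some light or recent smoking will be missed in patients still on patches. Verification would also be less strict in them than in patients off nicotine, so the number verified by each route should be reported by arm.

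### No questionnaire is listed between discharge and month 3, although withdrawal and adverse effects are to be followed throughout

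*Combined protocol and SAP*

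**What the plan says.** Specific objective 2 is to "Evaluate the symptoms and signs of withdrawal in the different groups throughout their follow-up". Specific objective 3 is to "Record the adverse effects of the different pharmacological therapies reported in the different groups throughout their follow-up". The outcome-variables section names withdrawal, craving and adverse-reaction questionnaires, but gives none of them a schedule or a recall period.

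The numbered procedures under Data Capture set the contacts:

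- **Item f (in hospital):** "questionnaires and measurements of exhaled CO and cotinine in urine are performed (treatment start day is day 0"). The same item adds: "The pharmacological treatment given to the subject will be for at least 12 weeks".
- **Item g (inpatient monitoring):** provision of medication. No form is listed.
- **Item h (discharge):** "an appointment is made at the Smoking Clinic within the first 14 days of discharge", with home treatment and advice. No form is listed.
- **Item j (first appointment):** "Processes: brief advice; intake of exhaled CO and cotinine in urine". It also schedules group CBT, "which lasts ten sessions, two times a week, with mixed modality (online or in-person").
- **Item k:** "Start CBT in the next two weeks after discharge". No form is listed.
- **Items l and m (second appointment):** placed at the end of therapy, given as 3 months from discharge. Questionnaires are listed.
- **Items o and q (6 and 12 months):** questionnaires are listed.

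The Results analysis plan foresees a comparison of the 2 groups and states that there is no blinding.

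**The concern.** Items f, m, o and q each pair questionnaires with CO and cotinine. Item j keeps the advice and both tests but drops the questionnaires. Because the entries are otherwise parallel, the omission is visible and not just a matter of brevity.

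The affected stretch is the one in which participants take study treatment at home. Two of the four specific objectives depend on these forms. Without a form at the first appointment, the listed information on withdrawal, craving and adverse reactions after discharge starts at month 3. Participants would then be looking back over about three months, knowing which treatment they were assigned. Anyone lost before month 3 would contribute no scheduled post-hospital form to either objective. Such data cannot be collected prospectively once the period has passed.

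**Working it through.** The plan gives no figure of its own here, so the check is date arithmetic on the listed schedule.

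**Inputs**

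- Minimum course: 12 weeks × 7 = 84 days, with day 0 the start of treatment in hospital (item f).
- First appointment: 0 to 14 days after discharge (item h).
- Second appointment: 3 months after discharge (item l). Three calendar months are 89 to 92 days, depending on the date. No visit window is stated.
- CBT: ten sessions, two a week (item j), starting 0 to 14 days after discharge (item k).
- Stay after day 0: L days. The documents do not give L.

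**Step 1. Gap from discharge to the next listed form.** The forms listed after item f are in item m, so the gap is 89 to 92 days. 89/7 = 12.7 and 92/7 = 13.1, or about 13 weeks.

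**Step 2. Home treatment covered by the gap.** On the minimum course, home treatment lasts 84 − L days after discharge. For any L of 0 or more this is at most 84, and 84 < 89. All home treatment on a 12-week course therefore falls inside the gap, with no assumption about L.

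**Step 3. If drug treatment runs to month 3 instead.** Home treatment then lasts 89 to 92 days and the form falls at its end. There is still no listed form between discharge and that point.

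**Step 4. Participants lost early.** The sample-size section allows for 25% loss: 67 − 50 = 17 per group. When these losses occur is not stated. Under that allowance, anywhere from 0 to 17 per group could leave before month 3.

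**Step 5. What remains if forms are added at the first appointment.** From that appointment to the month-3 form is 89 − 14 = 75 days at the shortest and 92 − 0 = 92 days at the longest.

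**Step 6. What an extra adverse-reaction form at the tenth CBT session would do.** At two sessions a week, the ninth falls 4 weeks (28 days) after the first, and the tenth 1 to 6 days later, so 29 to 34 days after the first. Adding a start 0 to 14 days after discharge puts the tenth session 29 to 48 days after discharge. The stretch from there to month 3 is 89 − 48 = 41 to 92 − 29 = 63 days.

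**The case against.** The strongest reply is that this is a short outline. It says only that questionnaires are given and never states which one at which visit, so both ends of the gap are inferred. Objective 3 speaks of effects that are reported, which could happen at any contact, and the plan has a clinic visit and ten CBT sessions in the period. Following participants throughout sets no frequency, and forms at 3, 6 and 12 months match the time points of objectives 1 and 4.

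Part of this stands. The instruments are not assigned, and spontaneous reports are not ruled out. But however generously the word is read at the other visits, it does not appear in item j. No step at the first appointment or in CBT lists recording symptoms, and unstructured reports are a weak basis for comparing arms. The only annex mentioned concerns contraindications.

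Two stronger readings are tempting, and the documents support neither:

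- **A reader might infer that the month-3 form always comes after treatment has ended.** With an assumed stay of 0 to 21 days, it would fall 89 + 0 − 84 = 5 to 92 + 21 − 84 = 29 days after a 12-week course. But 12 weeks is a minimum, and item l ties month 3 to the end of therapy. By Step 6, CBT sessions would finish 29 to 48 days after discharge, so that phrase may well mean drug treatment.
- **A reader might infer that no form is given at all after day 0 while on treatment.** In item f, day 0 defines the treatment clock and does not date the questionnaires. They may be given, or repeated, later in the stay.

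**Conclusion.** The point holds as a gap in what the schedule lists. From discharge to month 3, 89 to 92 days, no questionnaire is listed, and this covers all home treatment on the minimum course. That result rests on reading items g to k as written and on month 3 falling at its nominal date. It does not rest on the length of stay.

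Whether the month-3 form is on or off treatment cannot be settled from the text, because items f and l can be read together in more than one way. The number of participants affected, and the size and direction of any under-count, cannot be determined from the documents.

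The primary outcome, abstinence at 12 months, is unaffected. This is a cheap improvement to two specific objectives and not a flaw in the main comparison.

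**What to change.** 1. Add the existing withdrawal, craving and adverse-reaction questionnaires to the first Smoking Clinic appointment (item j). If they are already given there, item j only needs to say so.
2. Record the date of each form, with days since day 0 and days since discharge. The first appointment can fall anywhere from day L to day L + 14 of treatment, so the visit label alone does not say how long a participant had been treated.
3. Report the results descriptively by randomised arm, with the number who answered and the spread of days since day 0.
4. Reconcile the minimum treatment duration in item f with the end of therapy in item l, so that each month-3 form can be labelled as on or off treatment.
5. Optionally, repeat the short adverse-reaction form at one existing CBT session, for example the tenth, in a format that also works online. Participants who miss the session would give no second reading.

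**Cost:** three existing forms at one existing visit and the matching database entries, made by the researchers who already capture the data. No new visit or procedure is needed. The burden on patients and data entry rises slightly. With the first-appointment forms alone, 75 to 92 days still pass before the month-3 form. The optional CBT form would shorten the last stretch to 41 to 63 days, for adverse reactions only.
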